#### IV. Drugs/Substances/Devices

- A. Drugs will not be used in this trial. Instead, subjects will be given osteopathic manipulative treatment, BEMER therapy, and placebo light touch.
- B. The device utilized is BEMER Pro set.

### **Research Participants**

The target population is LECOM-Bradenton faculty, staff, osteopathic medical, dental, pharmacy, and master's students who are currently experiencing neck pain. The study will not target participants from a vulnerable or at-risk population. Our target population will be informed via email of the opportunity to participate in the research study and will be given the contact information to confirm eligibility with a study coordinator.

#### I. Inclusion

A. LECOM-Bradenton faculty, staff and Students currently enrolled in LECOM-Bradenton's osteopathic medical program, pharmacy program, dental program, and master's program who are currently experiencing neck pain will be approached for recruitment.

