    - k) Counterstrain technique for the following muscles/locations: Medial pterygoid, Anterior C7, Anterior C8, Posterior C1 inion
  3. Second year osteopathic medical students will perform the duties of diagnosing and screening for somatic dysfunction in these regions (as listed above). These same 4-6 students will also be trained to perform all of the treatment modalities by the osteopathic principles and practice (OPP) course director and OPP clinical faculty at LECOM-Bradenton.
  4. Explanation of each Osteopathic Manipulative Treatment (OMT) technique and screening tests
    - a) Myofascial release (MFR) is a system of diagnosis and treatment which engages continual palpatory feedback to achieve release of myofascial tissues [25]. MFR can be performed in a direct or indirect manner. If direct MFR is being performed the area of myofascial tissue restriction is engaged for the myofascial tissues and the tissue is loaded with a constant force until tissue release occurs. If indirect MFR

is being performed the area of the body with dysfunctional myofascial tissues are guided along the path of least obstruction until free movement is achieved. For this study, the student doctors will perform MFR in the suboccipital and cervical regions with the patient lying on their back.

b) Soft tissue (ST) is a system of diagnosis and treatment directed toward tissues other than bony or joint origins [25]. Soft tissue technique involves direct engagement of myofascial tissues and is applied with lateral stretching, linear stretching, deep pressure, traction and/or separation of muscle origin and insertion while monitoring tissue response and motion changes by palpation. Soft tissue techniques will be applied to the cervical and thoracic regions in this study.

c) Muscle energy (ME) is a form of osteopathic manipulative diagnosis and treatment in which the patient's muscles are actively used on request, from a precisely controlled position, in a specific direction, and against a distinctly executed physician counterforce [25]. We will use muscle energy technique in the cervical spine and thoracic regions in the supine position in this study.

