### III. Analysis

#### A. Study Statistics

1. Primary outcome variable
  - a) Questionnaire ratings before and after treatments
    - (1) Neck Disability Index (Appendix E) [28-31]
    - (2) SF-12 Health Survey (Appendix F) [32]
    - (3) Visual Pain Analog (Appendix C) [33]
2. Statistical plan including sample size justification and interim data analysis
  - a) Paired T-tests (N~10 subjects) to investigate the changes in neck pain after each treatment protocol.
  - b) One-Way ANOVA to investigate any statistically significant differences between the means of each of the 4 experimental groups.
3. Early stopping rules

- a) Any adverse effect, as determined by the attending licensed osteopathic physician. No adverse effects are anticipated.
- B. Blinding
  - 1. All outcome analyses will be performed in a blinded fashion. Subject survey and corresponding data will be de-identified and analyzed retrospectively by investigators with no exposure to the treatment sessions. Doing so will eliminate bias associated with investigator self-interest and ensure subject anonymity.

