#### II. Exclusion

A. Subjects will be excluded if they are unable to provide informed consent, are currently pregnant, have a positive screening test (listed above) or have a known medical history of any of the following:

1. Psychiatric conditions
2. Skin disorders or open wounds precluding skin contact
3. Fasciitis or fascial tears
4. Myositis
5. Neurological symptoms such as numbness, tingling, weakness in upper extremities
6. Neoplasia
7. Bone fracture, osteomyelitis, or osteoporosis
8. Coagulation problem
9. Deep vein thrombosis
10. Adrenal diseases/syndromes
11. Acute upper or lower respiratory infection
12. Immunosuppressive syndromes
13. Radiation or chemotherapy within the past 3 years
14. Lupus
15. Osteopenia
16. Congestive heart failure
17. BMI greater than 30

18. Any other autoimmune disease not stated above
  19. Medication changes within the last 4 weeks
  20. Asthma exacerbations within the last 4 weeks
  21. Immunosuppressive therapy as a consequence of organ transplantation
  22. Immunosuppressive therapy as a consequence of allogeneic cellular transplantations or bone marrow stem cell transplantation
  23. Other conditions often requiring immunosuppressive therapy
  24. Anticoagulant therapy
  25. Known sensitivity to the carotid sinus reflex
  26. Advanced carotid disease
  27. Down syndrome
- B. Subjects will be screened for eligibility based on the inclusion and exclusion criteria described above at the point of subject consent. No protected health information will be collected from subjects who are not eligible to participate in the study.
- C. If subjects develop any of the above issues during the course of the study, they will be removed from the study without penalty and will still receive compensation.
- D. All female patients will be screened in the selection process by self-report as to whether or not they are pregnant. Under any suspicion of pregnancy, the participant will be ineligible for participation.
- III. Definition of treatment failure or subject removal criteria
- A. Subjects who do not adhere to the full treatment regimen will be removed from the study.
- B. Subjects who experience any adverse effects from treatment, as determined by a licensed osteopathic physician, will be immediately removed from the study. However, we do not anticipate any adverse effects during the study. Last year we have successfully utilized OMT and the BEMER therapy without any adverse effects in a prior study on low back pain.

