## **Appendices**

### **Appendix A: Recruitment email**

The LECOM Student American Academy of Osteopathy (SAAO), is conducting a study, and we would like to welcome all LECOM faculty, staff, and students to participate. The study will evaluate the individual and combined impact of osteopathic manipulative treatment (OMT) and Bio Electro-Magnetic Energy Regulation (BEMER) therapy on neck pain.

This study will take place over a three-week period. Each subject in the OMT group will receive treatment 3 times per week for a period of 3 weeks. Subjects in the BEMER groups will receive treatment 5 times per week for a period of 3 weeks. Each subject in the OMT+BEMER group will receive OMT 3 times per week and BEMER therapy 5 times per week for a period of 3 weeks. Subjects will complete brief questionnaires regarding neck pain and quality of life before the beginning of study and will complete the same questionnaires following the completion of the three week treatment. Each treatment will be individually scheduled with your assigned study coordinators. Each treatment session will last approximately 10-30 minutes.

You will be compensated with a \$50 gift card for your time.

If you are interested and would like to learn more about the study, please contact [name] at [[contact]](mailto:[contact]) for more information.

Thank you for your consideration in helping with this very important research.

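### No listed eligibility criterion keeps study personnel out, so the student treaters and the LECOM-Bradenton faculty who train them may enrol and rate their own outcomes

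*Combined protocol and SAP*

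**What the plan says.** Research Participants, I. Inclusion, approaches LECOM-Bradenton "faculty, staff and Students currently enrolled in" its medical, pharmacy, dental and master's programmes, if they have neck pain at the time. The email in Appendix A announces that "The LECOM Student American Academy of Osteopathy (SAAO), is conducting a study" and adds that "we would like to welcome all LECOM faculty, staff, and students to participate".

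Research Participants, II. Exclusion, item A, removes people who cannot consent, who are pregnant, or who "have a positive screening test (listed above) or have a known medical history of any of the following"; a list of 27 medical items follows. Item B says that eligibility is judged on these inclusion and exclusion criteria when consent is taken.

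On who runs the trial, Methodology I.D.3 states that "Second year osteopathic medical students will perform the duties of diagnosing and screening for somatic dysfunction". The same item puts their number at 4–6, has them trained to give all the treatments, and names the osteopathic principles and practice course director and clinical faculty at LECOM-Bradenton as trainers.

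The placebo (Methodology I.F) is light hand contact without pressure, plus lying on a BEMER mat that is not switched on. The primary outcomes (Methodology III.A) are the Neck Disability Index, the SF-12 and a pain VAS, before and after treatment. Under Methodology III.B the data are to be "analyzed retrospectively by investigators with no exposure to the treatment sessions", which the plan presents as its protection against investigator self-interest.

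**The concern.** The people who deliver the trial and the people who may join it are drawn from the same college, and nothing in the listed criteria separates them. A student who has been taught the sham, or a faculty member who teaches it, would recognise it on receiving it. The subject is also the outcome assessor, because all three primary instruments are self-completed.

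Randomization does not remove this problem. It balances the number of insiders on average, but an unblinded subject's rating can depend on the arm received: more improvement reported on active treatment, less on sham. That bias adds to the contrast between arms even when insiders are evenly spread. Blinded analysis acts after the ratings have been given and cannot undo it. With about 10 subjects per arm, one such person is not negligible.

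**Working it through.** **1. Who falls inside the eligible population.** Setting the role descriptions beside the inclusion rule:

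- Student treaters and screeners (Methodology I.D.3): enrolled second-year osteopathic medical students. Inside, if they have neck pain and pass the medical criteria.
- OMT trainers (Methodology I.D.3; Risks and Benefits, I.B): LECOM-Bradenton faculty. Inside, on the same condition. Their number is not stated.
- BEMER trainer (Methodology I.C.2): a company representative. Not shown to be inside.
- Coordinators: affiliation not stated. Not shown either way.
- Analysts (Methodology III.B): must have had no contact with treatment sessions, which a treated subject could not satisfy. The eligibility criteria do not repeat or enforce this condition.

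No inclusion or exclusion item refers to a study role.

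**2. Arm size.** Methodology III.A gives about 10 subjects and four groups: 4 × 10 = 40. The budget agrees: $2,000 / $50 = 40. The figure of 10 cannot be re-derived, because no alpha, power, effect size or SD is given. Equal arms of 10 are assumed below.

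**3. Possible share of treaters.** The lower bound is 0. The upper bound, if every treater enrolled, is 4/40 = 10% to 6/40 = 15%. As a middle case, the Review of Literature gives an annual neck-pain prevalence of 30%. If that applied to these students (an assumption), 0.30 × 4 = 1.2 and 0.30 × 6 = 1.8 people would have neck pain within a year. That is 1.2/40 = 3% to 1.8/40 = 4.5% of the sample, before exclusions and willingness to join. The inclusion rule asks for current pain, so an annual figure would tend to overstate the number.

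**4. Weight of one person.** With k insiders in an arm of n, each with a biased VAS change of b mm, the arm mean moves by k × b / n. With n = 10 and b assumed to be 10–30 mm:

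- k = 1: 1–3 mm
- k = 2: 2–6 mm
- k = 3: 3–9 mm

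One insider in an active arm and one in placebo, biased in opposite directions by 20–30 mm each, move the contrast by 2 × 20/10 = 4 mm to 2 × 30/10 = 6 mm. The documents give no value for b. The shift must be in the change from baseline: someone who over-rates equally before and after adds nothing to a pre–post difference.

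**5. Chance imbalance.** With m insiders among 40, the probability of i in a given active arm and j in placebo is C(10,i) × C(10,j) × C(20,m−i−j) / C(40,m). Summing over |i − j| ≥ 2:

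- m = 2: 2 × 45/780 = 11.5%
- m = 4: 27%
- m = 6: 36%

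So even a bias that did not depend on the arm would not reliably cancel if several insiders enrolled.

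**The case against.** The strongest reply is that this argues from silence. The consent form and the IRB application, which identifies the designated students, are not in the text available here, and either might bar study staff. Elsewhere the protocol writes of researchers and subjects as different people: treaters disclose to subjects that they are not licensed physicians, and a researcher explains the study at consent. The email is an invitation, not an admission rule. This stands to the extent that nothing shows insider enrolment to be intended. It does not supply the missing criterion, because the exclusion section says that eligibility is judged on the criteria it lists.

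A second reply is that insiders are a small part of a wider weakness: many eligible subjects have osteopathic training and might recognise the sham anyway. That is fair, and the change proposed here would not cure it. But those who deliver or teach this particular sham are the clearest case and the easiest to remove.

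Third, the millimetre figures are assumed, and the 4–6 mm contrast needs two biased insiders in opposite arms. That stands; the figures show scale only.

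A reader might also infer that coordinators, analysts and every trainer may enrol. The documents do not support that. An analyst who was treated would breach the blinding section, the coordinators' affiliation is not given, and the BEMER representative is not shown to belong to the college.

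**Conclusion.** The point holds for two groups: the 4–6 student treaters and screeners, and the LECOM-Bradenton faculty who train them. As the criteria are written, either may enrol with neck pain, could not be blind to a sham they deliver or teach, and would supply self-rated primary outcomes with a weight of one tenth in an arm of about 10.

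The number who would do so is unknown and may be zero; 10–15% of 40 is the ceiling for treaters alone and assumes that all of them qualify and join. It would be wrong to conclude that insiders were meant to enrol, or that the results will be shifted by any particular amount. For analysts the narrower statement is that the blinding section sets a condition which the eligibility criteria do not enforce.

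No stated sample size, test or treatment is wrong on this account. It is a cheap improvement, best made before recruitment, since insider ratings cannot be corrected once collected.

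**What to change.** Add to Research Participants, II.A, an exclusion such as: *any person with a role in this study (screening, treating, training, scheduling, randomizing, data handling or analysis), and anyone who attended the study's treatment or placebo training.* This also makes the analysts' condition in Methodology III.B enforceable at entry, and it settles the position of the coordinators whatever their affiliation.

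Change the email in Appendix A to invite LECOM-Bradenton faculty, staff and students *other than members of the study team*.

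The target of about 10 per arm and 40 in total stays as it is. The cost is one line in the protocol, one phrase in the email, and the loss of a few potential subjects from a college-wide pool.

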**Research Purpose:**

The purpose of this project is to investigate the individual and combined effects of Osteopathic Manipulative Treatment (OMT) and Bio Electro-Magnetic Energy Regulation (BEMER) Therapy on neck pain in adults.

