There have been conflicting reports that investigated the effects of spinal manipulation (an osteopathic manipulative technique) on neck pain [1, 14-22]. For example, patients with acute and subacute neck pain who received treatment with spinal manipulative therapy experienced significant pain relief compared with medication at 8, 12, 26, and 52 weeks, proving to be more effective for both short and long term pain relief [1]. On the other hand, Fredin & Loras suggested that combined treatment consisting of manipulation therapy and exercise therapy does not seem to be more effective in reducing neck pain intensity at rest, neck disability or improving quality of life in adult patients with grade I-II neck pain, than exercise therapy alone [18]. These discrepancies may be explained by differences in the specific therapeutic techniques, duration of the intervention, and characteristics of the sample population. It is clear that additional research investigating the effects of alternative treatments on neck pain is warranted.

Specific OMT approaches have been studied for the treatment of patients presenting with neck pain, but substantially less than other general complaints such as lower back pain [3, 23, 24]. In one study, it was demonstrated that treating somatic dysfunction of the cervical spine with OMT in patients with acute neck pain provides pain relief and significantly reduces pain intensity when compared to intramuscular administration of ketorolac tromethamine [21]. The authors concluded that OMT is a reasonable alternative to parenteral nonsteroidal anti-inflammatory medication for patients with acute neck pain [21]. In addition, a specific osteopathic manipulative treatment called muscle energy has been shown to provide significant relief of neck pain and improve cervical range of motion [20]. Although there is some evidence to suggest OMT may be an alternative to the treatment of neck pain [20, 21], there is a clear need to better understand the effects of OMT specifically on subacute and chronic neck pain.

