H. OMT, BEMER, and placebo will be performed by osteopathic medical students who have completed additional training given by a licensed osteopathic physician to ensure uniform technique. A licensed osteopathic physician will be in the vicinity of the treatment location at all times while treatments are being given.

I. All data collection logs will be de-identified of personal information and only contain the randomized participant ID number linking the participant to the data collected.

J. The identifying information will be maintained by the principal investigator in a locked cabinet, which they alone have access to.

II. Study Procedures and Timeline

A. Study duration

1. The study duration is three weeks. The subjects will be required to have either OMT, BEMER, OMT+BEMER, or Placebo treatments during the course of the study. Each subject in the OMT groups (i.e. OMT and OMT+BEMER) will receive treatment 3 times per week for a period of 3 weeks. Subjects in the BEMER groups (i.e. BEMER and OMT+BEMER) will receive treatment 5 times per week for a period of 3 weeks. Finally, subjects in the Placebo group will receive the combined light touch and BEMER sham treatments at same intervals as the corresponding experimental groups. OMT, BEMER, and placebo treatments will be performed by osteopathic medical students who have completed additional training given by a licensed osteopathic physician, to ensure uniform technique.
2. Recruitment:
  - a) LECOM-Bradenton faculty, staff, osteopathic medical, dental, pharmacy, and master's students will be informed via email of the opportunity to participate in the research study and will be given contact information to confirm eligibility with a study coordinator (Appendix A).
3. Experimental Sessions
  - a) Following written consent (Appendix B), subjects will be given a randomized study ID number. They will be randomized into their treatment group.

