  - b) Each subject in the OMT groups (i.e. OMT and OMT+BEMER) will receive treatment 3 times per week for a period of 3 weeks. As previously mentioned, subjects in the BEMER groups (i.e. BEMER and OMT+BEMER) will receive treatment 5 times per week for a period of 3 weeks. Finally, subjects in the Placebo group will receive the combined light touch and BEMER sham treatments at same intervals as the corresponding experimental groups. OMT, BEMER, and placebo treatments will be performed by osteopathic medical students who have completed additional training given by a licensed osteopathic physician, to ensure uniform technique. All treatments will be performed during the span of three consecutive weeks.
  - c) Subjects will complete brief questionnaires regarding neck pain and quality of life before the beginning of study and will complete the same questionnaires following the completion of the three week treatment (Appendices C, E, F).

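### Neck pain of any duration is eligible although the OMT rationale points to subacute and chronic pain, and duration is used in neither the randomisation nor the analysis

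*Combined protocol and SAP*

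**What the plan says.** **Rationale.** After citing OMT results in acute pain, the Review of Literature concludes that "there is a clear need to better understand the effects of OMT specifically on subacute and chronic neck pain".

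**Purpose and population.** The Research Purpose is to "investigate the individual and combined effects of Osteopathic Manipulative Treatment (OMT) and Bio Electro-Magnetic Energy Regulation (BEMER) Therapy on neck pain in adults", with no limit on duration. Research Participants describes the target in the same way, and Inclusion I.A takes members of the institution "who are currently experiencing neck pain will be approached for recruitment". No minimum or maximum duration is set.

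**Exclusions.** None of the 27 listed items concerns how long the episode has lasted. The nearest is item 19, "Medication changes within the last 4 weeks", which would remove a new episode only if it had led to a change of medication.

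**Timing.** Methodology II.A.1: "The study duration is three weeks". Under II.A.3 subjects complete questionnaires at baseline and "will complete the same questionnaires following the completion of the three week treatment". No other outcome assessment is planned.

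**Allocation and analysis.** Methodology I.C.3 and II.A.3.a randomise subjects to four groups and mention no stratification. Analysis III.A.2 plans paired t-tests with about 10 subjects and a one-way ANOVA across the four groups, with no covariate.

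**The concern.** Someone whose neck became sore two days ago and someone in pain for two years are equally eligible and count equally. Over three weeks the two may change by different amounts for reasons unrelated to treatment. That difference then sits in the error term of the ANOVA. With about 10 per arm and unstratified allocation, one arm can also receive more recent cases than another by chance.

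The second issue is interpretation. The result will describe a mixture, and the plan has no step that relates it to the subacute and chronic pain for which the OMT rationale asks for evidence. Onset that is not recorded at baseline can later be recovered only by recall, and stratification cannot be added after randomisation.

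**Working it through.** **The plan's own figure.** About 10 per group in four groups is 4 × 10 = 40, which agrees with the 40 in the budget (Payment and Costs, II). No alpha, power, effect size or SD is given, so the figure of 10 cannot be derived.

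**Inputs.** From the documents: about 10 per arm, and a 100 mm VAS (Appendix C). Assumed, because the documents give no figures: equal allocation; SD of change of 20 mm within each pain type; a share *a* of recent cases of 20%, 30% or 50%; and a gap *g* between recent and longer-standing cases in mean three-week change, the same in every arm, of 15 or 30 mm.

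**Step 1: added variance.** SD of change = √(20² + g²·a(1−a)). For g = 30 and a = 30%: √(400 + 900 × 0.21) = √589 = 24.3 mm.

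**Step 2: standard error of a two-arm difference.** SE = SD × √(2/10). With no mixture, 20 × 0.447 = 8.9 mm. For g = 30 and a = 30%, 24.3 × 0.447 = 10.9 mm.

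**Step 3: the part due to chance imbalance.** This is g·√(2a(1−a)/10). For g = 30 and a = 30%: 30 × √0.042 = 6.1 mm. It is not additional to step 2, since 8.9² + 6.1² ≈ 10.9² (80 + 37.8 = 117.8). Imbalance and inflated SD are two descriptions of one variance term.

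| g (mm) | a | SD of change (mm) | SE, two arms (mm) | of which imbalance (mm) | variance ratio to 20² |
|---|---|---|---|---|---|
| 0 | any | 20.0 | 8.9 | 0 | 1.00 |
| 15 | 20% | 20.9 | 9.3 | 2.7 | 1.09 |
| 15 | 30% | 21.1 | 9.5 | 3.1 | 1.12 |
| 15 | 50% | 21.4 | 9.6 | 3.4 | 1.14 |
| 30 | 20% | 23.3 | 10.4 | 5.4 | 1.36 |
| 30 | 30% | 24.3 | 10.9 | 6.1 | 1.47 |
| 30 | 50% | 25.0 | 11.2 | 6.7 | 1.56 |

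The last column is also the factor by which the required sample size rises. At g = 30 and a = 30%, removing this variance would be worth about as much as going from 10 to 10 × 1.47 ≈ 15 per arm.

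**Step 4: power, with treatment equally effective in both types.** Take a standardised effect of 0.8, which is 16 mm on an SD of 20. Two-sided 5% power for one pair of arms of 10 is 39.5%. With the SD at 24.3 mm the effect becomes 16/24.3 = 0.66 and power about 29%.

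**Step 5: dilution, only under a further assumption.** If recent cases have no treatment contrast at all, the pooled effect is (1−a) times the effect in longer-standing pain: 80%, 70% or 50% for a = 20%, 30% or 50%. With the SD held fixed, power at 0.8 falls from 39.5% to 27.3%, 21.9% or 13.3%. Equal recovery in all arms does not produce this by itself: it cancels from the mean difference and leaves only steps 1 to 3.

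**The case against.** A reader might infer that the trial enrols the wrong population. The documents do not support that: title, purpose, target population and inclusion criterion all cover current neck pain in adults. The sentence on subacute and chronic pain is motivation in a literature review, and it concerns OMT only. The same review says BEMER has not been studied in neck pain, so for BEMER the gap is open at every duration, and two of the three active arms contain BEMER.

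A reader might also infer that recent cases settle in every arm and so dilute the effect. The documents give neither a share of recent cases nor a recovery rate, and their own evidence points the other way. One cited trial concluded that "OMT is a reasonable alternative to parenteral nonsteroidal anti-inflammatory medication for patients with acute neck pain", and another reported more relief with manipulation than with medication in acute and subacute pain from 8 to 52 weeks. Zero contrast in recent cases is therefore purely an assumption. If it held, the gap in an active arm would also shrink: with an assumed 15 mm effect confined to longer-standing pain and a = 30%, the active-arm SD would be √(400 + 15² × 0.21) = 21.1 mm rather than 24.3.

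Nor can it be said that the data could not separate recent from long-standing pain. Material between Appendices C and E is not in the available text, so whether a form asks about onset cannot be checked. Finally, admitting all comers is a legitimate choice in a small study, and power is low with or without recent cases.

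These objections stand against the stronger readings. They leave in place that the plan as written uses duration in neither allocation nor analysis, and that the rationale and the inclusion criterion differ without explanation.

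**Conclusion.** The point holds as a mismatch between the OMT rationale and eligibility, together with an avoidable loss of precision. Its size depends on assumptions: nothing if recent and longer-standing pain change alike, a 9% to 14% rise in variance with a 15 mm gap, and a 36% to 56% rise with a 30 mm gap, for recent shares of 20% to 50%. Dilution of the treatment effect is possible but not established. The trial can answer its stated question about neck pain in adults. What it cannot do, as planned, is attribute the answer to subacute and chronic pain.

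This is a worthwhile improvement and not a flaw that invalidates the design. Even with no recent cases, 80% power for one pair of arms of 10 needs a standardised effect of about 1.32.

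**What to change.** 1. Record the date of onset of the current episode on the baseline form, before randomisation.
2. Stratify the randomisation by recent versus longer-standing pain at a cut-off that the sponsor defines and justifies. Conceal the list and preferably vary the block size. With four arms, a fixed block of 4 makes the last assignment predictable to anyone who knows the previous three.
3. In Analysis III.A.2.b, add duration as a factor in the between-arm comparison.
4. State conclusions for neck pain of mixed duration, or reconcile the Review of Literature with Inclusion I.A. Which of the two to change is for the sponsor. Exclusion item 19 offers no support for a duration limit, since its four-week window concerns medication.

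**Cost.** One baseline question, a slightly more complex allocation list and one error degree of freedom (40 − 4 = 36 becomes 35). A small stratum may end with an incomplete block: at an assumed 30% share, about 12 of 40 subjects, or 3 per arm, would be recent cases. No volunteer is turned away. The change does not make 10 per arm adequate, and it does not help the within-arm paired t-tests, which cannot tell recovery from treatment benefit.
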